#### **4.3.2 Design rationale for Long-Term Open-Label Extension – amended**

Due to the clinical efficacy of rivaroxaban 2.5mg bid + aspirin 100mg od (see Section 1.2.4), participation in the LTOLE will be offered to all subjects who meet the LTOLE Inclusion/Exclusion criteria defined in Section 5.1.3.

#### **4.4 Final follow-up visit and end of study-amended**

The primary analysis will be based on the events that occur between randomization and the Final Follow-up Visit. The date of the Final Follow-up Visit cannot be pre-determined as this study is event-driven but the visit will occur when at least 2,200 subjects experience an event

---

 “ticagrelor” added as per Amendment 8 based upon the recently published PEGASUS trial.

 Sentence revised as per Amendment 8. (See Section 13.2.2.)

 Text added as per Amendment 11. (See Section 13.3.1)

for the primary efficacy outcome. All subjects will remain in follow-up until this minimum number of primary outcome events has been reached, irrespective of whether they are still taking study treatments or whether they have experienced an outcome. The Final Follow-up Visit and the subsequent 30-day washout period will occur nearly simultaneously (as scheduling permits) for all study subjects.

For each participating European Union (EU) country, the end of the study according to the EU Clinical Trial Directive will be reached when the telephone call at the end of the 30 day washout period for the last subject for all centers in the respective country has occurred. The end of the study as a whole will be reached as soon as the end of the study according to the above definition has been reached in all participating countries (EU and non-EU).

### **Long-Term Open-Label Extension – amended**

The final visits of LTOLE will begin, per country, when the duration reaches 3 years from the regulatory approval of LTOLE or the rivaroxaban treatment is commercially available for this indication in the respective country, whichever comes first. The subject should be called in for the final visit within approximately 3 months or at latest the final visit may be conducted at the next scheduled visit.

## **5. Study population - amended**

Multiple strategies will be employed to identify subjects potentially eligible for this study. These will include (but are not restricted to) database screening, chart screening, and patient screening at physician offices and at internal medicine, cardiology, and vascular disease/imaging clinics. The approach at individual centers will vary according to physician, office, or hospital environment, and ethical considerations.

Approximately 28,300 eligible subjects will be admitted to the run-in period and an additional 2000 will be enrolled post CABG and without run-in. Approximately 10% of run-in subjects are expected to either be non-compliant with treatment or to decline further interest in participating; thus, the study will randomize approximately 27,400 men and women with objectively confirmed CAD or PAD from approximately 33 countries worldwide.

Subjects with high risk of incident cardiovascular disease will be enrolled in the study. Subjects will be treated with rivaroxaban, the combination of rivaroxaban and aspirin, or aspirin on top of usual care. Investigators in the study are selected based on their qualifications and ability to enroll and treat these subjects in accordance with the protocol and applicable standard of care.

For the purpose of determining eligibility for this trial, subjects meeting criteria for CAD must have one or more of the following:

- Myocardial infarction within the last 20 years, or

---

 Text added as per Amendment 11. (See Section 13.3.1)

 Text modified/added as per Amendments 6 and 8. (See Sections 13.1.2 and 13.2.2.)

 Text modified as per Amendment 6. (See Section 13.1.2)

- Multi-vessel coronary disease\* with symptoms or history of stable or unstable angina, or
- Multi-vessel percutaneous coronary intervention (PCI), or
- Multi-vessel CABG surgery

\*Refers to stenosis of greater than or equal to 50% in 2 or more coronary arteries, confirmed by invasive coronary angiography, or non-invasive imaging or stress studies (e.g. exercise or pharmacologic) suggestive of significant ischemia in 2 or more coronary territories; or in 1 coronary territory if at least one other territory has been revascularized

For the purpose of determining eligibility for this trial, subjects meeting criteria for PAD must have one or more of the following:

- Previous aorto-femoral bypass surgery, limb bypass surgery, or percutaneous transluminal angioplasty revascularization of the iliac, or infrainguinal arteries, or
- Previous limb or foot amputation for arterial vascular disease (i.e., excludes trauma), or
- History of intermittent claudication and one or more of the following: 1)  an ankle/arm blood pressure (BP) ratio < 0.90, or 2)  significant peripheral artery stenosis ( $\geq 50\%$ ) documented by angiography, or by duplex ultrasound, or
- Previous carotid revascularization (e.g., endarterectomy, stenting) or asymptomatic (i.e., no ipsilateral stroke or transient ischemic attack within 6 months) carotid artery stenosis  $\geq 50\%$  as diagnosed by duplex ultrasound or angiography.

## 5.1 Eligibility – amended

In order to be eligible for study entry, potential subjects must meet all of the inclusion criteria and none of the exclusion criteria listed below.

### 5.1.1 Inclusion criteria - amended

- Willing and able to provide written informed consent
- Meet criteria for CAD\* and/or PAD
- \*Subjects with CAD must also meet at least one of the following criteria:
- Age  $\geq 65$ , or
- Age <65 and documented atherosclerosis or revascularization involving at least 2 vascular beds, or at least 2 additional risk factors:
  - 1) Current smoker (within 1 year of randomization)
  - 2) Diabetes mellitus
  - 3) Renal dysfunction with estimated glomerular filtration rate <60 ml/min

 Text modified/added as per Amendment 6. (See Section 13.1.2)

- 4) Heart failure
- 5) Non-lacunar ischemic stroke  $\geq 1$  month ago

§ Because CAD involves disease in the coronary vasculature, only one additional vascular bed is required: e.g. the aorta and arterial supply to the brain, gastro-intestinal tract, lower limbs, upper limbs, or kidneys.

### 5.1.2 Exclusion criteria - amended

- High risk of bleeding
- Stroke within 1 month or any history of hemorrhagic or lacunar stroke
- Severe heart failure with known ejection fraction  $<30\%$  or New York Heart Association (NYHA) class III or IV symptoms
- Estimated glomerular filtration rate (eGFR) $<15$  mL/min
- Need for dual antiplatelet therapy, other non-aspirin antiplatelet therapy, or oral anticoagulant therapy
- Known non-cardiovascular disease that is associated with poor prognosis (e.g., metastatic cancer) or that increases the risk of an adverse reaction to study interventions.
- History of hypersensitivity or known contraindication for rivaroxaban, aspirin, pantoprazole, or excipients, if applicable.
- Systemic treatment with strong inhibitors of both CYP 3A4 and p-glycoprotein (P-gp) (e.g., systemic azole antimycotics, such as ketoconazole, and human immunodeficiency virus [HIV]-protease inhibitors, such as ritonavir), or strong inducers of CYP 3A4, i.e. rifampicin, rifabutin, phenobarbital, phenytoin, and carbamazepine
- Any known hepatic disease associated with coagulopathy
- Subjects who are pregnant, breastfeeding, or are of childbearing potential, and sexually active and not practicing an effective method of birth control (e.g. surgically sterile, prescription oral contraceptives, contraceptive injections, intrauterine device, double-barrier method, contraceptive patch, male partner sterilization)
- Previous assignment to treatment during this study
- Concomitant participation in another study with investigational drug
- Known contraindication to any study related procedures

An additional exclusion for the pantoprazole randomization is:

- Need for continuous treatment with a PPI

---

 Text modified as per Amendment 6. (See Section 13.1.2)

### 5.1.3 Long-Term Open-Label Extension – amended

All subjects from COMPASS trial will be invited to join LTOLE as long as they continue to meet the COMPASS eligibility criteria (refer to sections 5.1.1 and 5.1.2) plus the specific ones for LTOLE (refer to sections 5.1.3.1 and 5.1.3.2). All LTOLE subjects must provide written informed consent to participate in LTOLE.

#### 5.1.3.1 Inclusion criteria

- All subjects randomized to the COMPASS trial willing to consent to LTOLE are eligible unless the subjects developed a condition considered by the investigator as exclusionary.
- Subjects who have given their written informed consent to participate in the LTOLE after having received adequate information prior to any LTOLE specific procedures.

#### 5.1.3.2 Exclusion criteria

- Subjects should not be included if, in the judgement of the investigator, they have developed a condition which should exclude them from receiving LTOLE study medication. For example if the subject has developed atrial fibrillation or had a severe allergic rash while in the study, which subsided when drug was stopped and returned when drug was reinitiated.

## 5.2 Discontinuation of subjects from study treatment - amended

All subjects will be encouraged to remain on treatment and under observation for the full duration of the study. However, at any time during the study and without giving reasons, subjects may withdraw from the study at their own request or at the request of their legally acceptable representative. The subject will not suffer any disadvantage as a result. In all cases, the reason for permanent discontinuation of study treatments (including “at the subject’s request”) must be recorded in the case report form (CRF) and in the subject’s medical records.

It is important to note that discontinuation of study treatment is not the equivalent to withdrawal of informed consent. Additionally, withdrawal of consent does not withdraw permission to collect vital status. Withdrawal of this consent must be made separately. In cases where subjects indicate they do not want to “continue”, investigators must determine whether this refers to discontinuation of study treatment (the most common expected scenario), unwillingness to attend follow-up visits, unwillingness to have telephone contact, unwillingness to have any contact with study personnel, or unwillingness to allow contact with a third party (e.g., family member, doctor). **In all cases, including the subjects who have had any of the primary study outcome events, every effort must be made to continue to follow the subject at regular study visits. Additionally, survival status and outcome information must be determined for all subjects.**

---

 Text added as per Amendment 11. (See Section 13.3.1)

 Sentence revised as per Amendment 8. (See Section 13.2.2)

### 5.2.1 Replacement

No subject replacements are permitted in this study.

### 5.2.2 Long-Term Open-Label Extension – amended

In case of permanent discontinuation of LTOLE treatment, the subject should come for a final visit within approximately 3 months, but follow the PPI visit schedule if applicable.

### 5.3 Subject identification

Each subject will receive a unique identification number, which will represent both the assigned study center number and subject number. The center number will be pre-assigned by PPD. The subject identification number, consisting of center number and subject number must be entered in the PPD randomization and drug management system to obtain the assignment of study treatment. Once assigned to a subject, the subject identification number will not be re-used.

## 6. Treatments

### 6.1 Treatments to be administered - amended

The study drugs to be administered in this trial include the antithrombotic drugs, rivaroxaban and enteric-coated aspirin; the PPI pantoprazole; and their matching placebos.

#### 6.1.1 Run-in - amended

During the run-in period, Day -28 to Day -1, eligible subjects (excluding those who are randomized Day 4-7 after CABG surgery) who have signed informed consent and stopped non-study anticoagulants and aspirin will receive rivaroxaban placebo bid and aspirin 100 mg od. Study pantoprazole or pantoprazole placebo will not be administered during the run-in period.

All doses will be provided in tablet form for oral administration.

#### 6.1.2 Randomization - amended

Subjects who have completed the run-in period with adherence to treatment with rivaroxaban placebo bid and aspirin 100 mg od of at least 80% except for extenuating circumstances, and who wish to continue in the study will be randomized. Subjects being randomized after run-in and those who are being randomized Day 4-7 after CABG surgery (Section 7.1.1 Tabulated overview) and who do not have a continuous need to take a PPI, will initially be randomized 1:1 to receive pantoprazole 40 mg od or matching placebo od, stratified by center. All subjects will then be randomized 1:1:1 to anticoagulant therapy stratified by center and by PPI use (randomized to pantoprazole, randomized to pantoprazole placebo, not randomized because subject is already taking a PPI as shown below:

---

 Text added as per Amendment 11. (See Section 13.3.1)

 Text modified/added as per Amendment 6. (See Section 13.1.2)

 Text deleted as per Amendment 6. (See Section 13.1.2)

**Arm A:** rivaroxaban 2.5 mg bid + aspirin 100 mg od

**Arm B:** rivaroxaban 5.0 mg bid + aspirin placebo od

**Arm C:** rivaroxaban placebo bid + aspirin 100 mg od

All doses will be provided in tablet form for oral administration.

Follow-up will continue until a minimum of 2,200 subjects experience an event for the primary efficacy outcome for the rivaroxaban randomization. These events are expected to accumulate over approximately 4-5 trial years after randomization of the first subject.

### 6.1.3 Treatment in Long-Term Open-Label Extension – amended

The LTOLE treatment will be open-label rivaroxaban 2.5 mg bid + aspirin 100 mg od.

## 6.2 Identity of study treatment - amended

All study drugs will be labeled in the local language according to the requirements of local law and legislation and will include no information about the subject except for the medication number. Label text will be approved according to the sponsor's agreed procedures, and a copy of the labels will be made available to the study site upon request. For the purpose of this study, the term "aspirin" is used interchangeably with the term "acetyl salicylic acid".

For all study drugs, a system of numbering in accordance with all requirements of Good Manufacturing Practice (GMP) will be used, ensuring that each dose of study drug can be traced back to the respective bulk ware of the ingredients. Lists linking all numbering levels will be maintained by the sponsor's clinical supplies quality assurance (QA) group.

A complete record of batch numbers and expiry dates of all study treatment as well as the labels will be maintained in the sponsor study file.

## 6.3 Treatment assignment - amended

For subjects who successfully complete the run-in period, the investigator or delegate will access the PPD randomization and drug management system to confirm eligibility and compliance to run-in rivaroxaban placebo bid and aspirin od and to obtain the randomized treatment allocation.

The PPD randomization and drug management system will assign the subject a unique number for each medication that corresponds to one of the treatments listed in [Table 4-1](#).

### Long-Term Open-Label Extension – amended

All subjects in the LTOLE will receive the same treatment of rivaroxaban 2.5 mg bid + aspirin 100 mg od.

---

 Text added as per Amendment 11. (See Section [13.3.1](#))

 Text added as per Amendment 6. (See Section [13.1.2](#))

 Sentence revised as per Amendment 8. (See Section [13.2.2](#))

 Text added as per Amendment 11. (See Section [13.3.1](#))

## 6.4 Dosage and administration - amended

Study medication will be taken orally. Study rivaroxaban/rivaroxaban placebo is taken twice daily (generally morning and evening, approximately 12 hours apart) and study aspirin/aspirin placebo and study pantoprazole/pantoprazole placebo are taken once daily, generally in the morning. The first doses of study drug should be administered on the day of randomization, or at least 12 hours after the last dose of antithrombotic medication if being randomized post-CABG.

If a dose of study rivaroxaban/rivaroxaban placebo is missed and less than 6 hours have elapsed since the time that the missed dose was due, it should be taken immediately. If more than 6 hours have elapsed since the missed dose was due, the dose should be skipped and the next dose of study rivaroxaban should be taken according to schedule.

If a dose of study aspirin/aspirin placebo or study pantoprazole/pantoprazole placebo is missed it should be taken as soon as the subject becomes aware that the dose has been missed.

### 6.4.1 Dose modifications - amended

The investigator should interrupt study drug for a given subject if continuation is deemed to be detrimental to the subject's well-being. All subjects who interrupt study drug should resume treatment when possible. If there is concern that the subject may be intolerant of study treatments or if the subject is reluctant to take the full dose of study treatments, a possible approach to restarting study medications is to reduce the frequency of dosing (eg, to once-daily or alternate-daily). Irrespective of whether or not treatment is resumed, all subjects must be followed according to the study protocol until the end of the study.

Permanent study drug interruption should be recorded on the corresponding follow-up case report form, giving the date and primary reason for stopping the study drug. If one of the study treatments needs to be discontinued, other study treatments must be continued. For example, if study rivaroxaban/rivaroxaban placebo is interrupted, study aspirin/aspirin placebo and study pantoprazole/pantoprazole placebo should be continued.

### Long-Term Open-Label Extension – amended

No dose modifications will be conducted in the LTOLE.

### 6.4.2 Dose modifications and treatment guidance - amended

This section provides a general guide for investigators on the management of subjects who develop intercurrent illnesses or bleeding during the course of the COMPASS trial. The guidance provided in this section does not replace clinical judgment nor usual care in determining the appropriate management strategy for individual subjects. For specific treatment guidance with study pantoprazole/pantoprazole placebo see Section 6.9.4

---

 Sentence revised as per Amendment 8. (See Section 13.2.2)

 Sentence revised as per Amendment 8. (See Section 13.2.2)

 Text modified/added as per Amendment 6. (See Section 13.1.2)

 Text added as per Amendment 11. (See Section 13.3.1)

### **6.4.2.1 Guidance for the treatment of subjects who require an invasive procedure - amended**

If the subject requires an invasive procedure that is associated with a standard or high risk of bleeding (i.e., any procedure that is not considered “minor”), study rivaroxaban/rivaroxaban placebo must be interrupted. Study aspirin/aspirin placebo may also be interrupted, at the discretion of the investigator. If study aspirin/aspirin placebo is interrupted, non-study aspirin may be used.

#### **Dosing recommendations before and after invasive procedures and surgical intervention**

If an invasive procedure or surgical intervention is required, rivaroxaban/rivaroxaban placebo should be stopped at least 24 hours before the intervention, if possible and based on the clinical judgment of the physician. If the procedure cannot be delayed, the increased risk of bleeding should be assessed against the urgency of the intervention. Rivaroxaban/rivaroxaban placebo should be restarted after the invasive procedure or surgical intervention as soon as possible, provided the clinical situation allows and adequate hemostasis has been established.

If surgery is urgent or needed in an emergency situation, the risk of bleeding must be weighed against the risk of delaying surgery. The total daily dose of rivaroxaban in subjects randomized to receive 5 mg bid is equivalent to the prophylactic dose that was tested in major orthopedic surgery trials and this dose of rivaroxaban is not expected to substantially increase the risk of bleeding. The total daily dose of rivaroxaban in subjects randomized to receive rivaroxaban 2.5 mg bid is only half that of the orthopedic thromboprophylaxis dose although these subjects will also be receiving treatment with aspirin. If there is a concern about the risk of bleeding in a subject who requires urgent or emergency surgery, unblinding may be considered but should *only* be performed if knowledge of randomized treatment allocation will influence clinical management (Section 6.5). A two-unit single donor platelet transfusion in subjects treated with the combination of aspirin and rivaroxaban may restore the capacity to generate thromboxane and thereby overcome the antiplatelet effects of aspirin.

#### **Long-Term Open-Label Extension – amended**

The same guidance will apply to LTOLE.

### **6.4.2.2 Guidance for the treatment of subjects who require coronary artery bypass graft surgery – amended**

CABG surgery can occur immediately prior to randomization or it may occur in randomized subjects who later develop a need for the surgery.

Subjects who are scheduled to be randomized Day 4-7 after CABG surgery will not participate in the run-in phase (Section 4.1.1). Randomization should only be performed between Day 4-7 post-CABG and at least 24 hours following the removal of chest tubes.

---

 Text deleted as per Amendment 6. (See Section 13.1.2)

 Text added as per Amendment 11. (See Section 13.3.1)

Study drug should not be administered until at least 12 hours after last administration of any anticoagulant (including DVT prophylaxis).

Subjects who are scheduled for CABG surgery during the course of the trial ideally should interrupt study rivaroxaban/rivaroxaban placebo at least 24 hours before CABG surgery in order to minimize the risk of bleeding. Study aspirin/aspirin placebo may be interrupted and/or non-study aspirin may be used or at the discretion of the investigator. The timing of resumption of study antithrombotic therapy after surgery is at the discretion of the investigator but, in general, study rivaroxaban/rivaroxaban placebo or study aspirin/aspirin placebo should be resumed once the chest tubes are removed and hemostasis is secure. Study rivaroxaban/rivaroxaban placebo should be interrupted if subjects require in-hospital anticoagulant thromboprophylaxis. In all cases, the goal should be to resume study antithrombotic drugs within 14 days and prior to being discharged from hospital.

### **Long-Term Open-Label Extension – amended**

The same guidance will apply to LTOLE. For subjects who are scheduled to undergo CABG, LTOLE treatment can be initiated four days after CABG and at least 24 hours after the removal of chest tubes. LTOLE treatment should not be administered until at least 12 hours after last administration of any anticoagulant (including DVT prophylaxis).

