### **6.9.3 Anticoagulant treatment - amended**

Subjects who develop a need for anticoagulant therapy (e.g., thromboprophylaxis in subjects undergoing major orthopedic surgery, acute venous thromboembolism, atrial fibrillation, mechanical aortic valve replacement) must interrupt study rivaroxaban/rivaroxaban placebo. Study rivaroxaban/rivaroxaban placebo must be restarted in subjects who no longer have a need for non-study anticoagulant therapy (e.g., after completion of anticoagulant thromboprophylaxis or anticoagulant treatment for venous thromboembolism). In subjects who develop a need for anticoagulant therapy, study aspirin/aspirin placebo may also be interrupted, at the discretion of the investigator.

If prophylactic anticoagulation is required, subjects should start the first dose of open prophylactic anticoagulation at the time that the next dose of study rivaroxaban/rivaroxaban placebo is due. If study drug is interrupted and the subject is transitioned to an anticoagulant with a slow onset of action, bridging therapy may be needed.

If therapeutic anticoagulation is required, subjects should start therapeutic anticoagulation immediately, irrespective of the timing of the last dose of study rivaroxaban.

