### **Long-Term Open-Label Extension – amended**

**Subjects who develop a need for anticoagulant therapy** (e.g., thromboprophylaxis in subjects undergoing major orthopedic surgery, acute venous thromboembolism, atrial fibrillation, mechanical aortic valve replacement) must discontinue LTOLE medication. Guidance for converting see below:

- **Converting from rivaroxaban to oral anti-coagulants**

Rivaroxaban affects INR, so INR measurements made during co-administration with oral anticoagulant may not be useful for determining the appropriate dose of oral anticoagulant. One approach is to discontinue rivaroxaban and begin both a parenteral anticoagulant and oral VKA at the time the next dose of rivaroxaban would have been taken.

- **Converting from rivaroxaban to parenteral anti-coagulants**

Discontinue rivaroxaban and give the first dose of parenteral anticoagulant at the time that the next rivaroxaban dose would be taken.

**Study rivaroxaban can be restarted at the discretion of the investigator** in subjects who no longer have a need for non-study anticoagulant therapy (e.g., after completion of

---

 Text added as per Amendment 11. (See Section 13.3.1)

 Text deleted as per Amendment 6. (See Section 13.1.2)

 Text added as per Amendment 11. (See Section 13.3.1)

anticoagulant thromboprophylaxis or anticoagulant treatment for venous thromboembolism). Guidance for restarting see below:

- **Converting patients from VKAs to rivaroxaban**

When converting patients from VKAs to rivaroxaban, INR values will be falsely elevated after the intake of rivaroxaban. The INR is not valid to measure the anticoagulant activity of rivaroxaban, and therefore should not be used.

- **Converting patients from parenteral anticoagulant to rivaroxaban**

For patients currently receiving a parenteral anticoagulant, start rivaroxaban 0 to 2 hours before the time of the next scheduled administration of the parenteral drug (e.g. LMWH) or at the time of discontinuation of a continuously administered parenteral drug (e.g. intravenous unfractionated heparin).

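### Within LTOLE, Sections 6.4.2.2 and 6.9.3 give different earliest times for starting or restarting rivaroxaban in a post-CABG subject coming off a parenteral anticoagulant

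*Protocol*

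**What the plan says.** Two LTOLE passages in the Protocol, both current text, set the time from the last anticoagulant to rivaroxaban.

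- **Section 6.4.2.2, LTOLE paragraph (bypass surgery).** The main-trial guidance of that section is carried into LTOLE. It includes interrupting rivaroxaban when in-hospital anticoagulant thromboprophylaxis is needed. The paragraph adds: "For subjects who are scheduled to undergo CABG, LTOLE treatment can be initiated four days after CABG", provided the chest tubes have been out for at least 24 hours. It then sets a minimum gap: "LTOLE treatment should not be administered until at least 12 hours after last administration of any anticoagulant (including DVT prophylaxis".
- **Section 6.9.3, LTOLE part (anticoagulant treatment in general).** Subjects who come to need an anticoagulant stop LTOLE medication. Rivaroxaban may be restarted at the investigator's discretion once the need has passed, and completed thromboprophylaxis is one of the examples. For conversion from a parenteral drug the instruction is to "start rivaroxaban 0 to 2 hours before the time of the next scheduled administration of the parenteral drug", or, for an infusion, to start "at the time of discontinuation of a continuously administered parenteral drug".

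Section 6.4.2.2 does not mention 6.9.3. Section 6.9.3 does not mention bypass surgery or 6.4.2.2.

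**The concern.** Take an LTOLE subject who has bypass surgery and is given a parenteral anticoagulant in hospital, for prophylaxis or otherwise. Section 6.4.2.2 applies because of the operation. Section 6.9.3 applies because the subject is coming off a parenteral anticoagulant. One section sets a minimum gap after any anticoagulant. The other ties the first rivaroxaban dose to the end of an infusion or to the next scheduled parenteral dose. For some regimens no single time satisfies both.

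What is at stake is a safety instruction for patients a few days after cardiac surgery. Depending on which section a site consults, the same subject could receive rivaroxaban at times that differ by up to 12 hours or more.

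**Working it through.** The protocol states no figure to reproduce. The check sets the two rules side by side and works out the gap that each implies, measured from the last anticoagulant administration (for an infusion, from its stop) to the first rivaroxaban dose.

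**Inputs**

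- Section 6.4.2.2 LTOLE: gap of at least 12 h, any anticoagulant.
- Section 6.9.3 LTOLE, infusion: gap of 0 h.
- Section 6.9.3 LTOLE, intermittent dosing: rivaroxaban is given d hours before the next parenteral dose, with d from 0 to 2. If the dosing interval is I hours, gap = I − d, which runs from I − 2 to I.
- I is not given in the protocol. Values of 8, 12 and 24 h are assumed here to show the range.

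**Results**

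| Parenteral regimen | Gap under 6.9.3 LTOLE | Gap under 6.4.2.2 LTOLE | Shortfall against 12 h | Can both be met? |
|---|---|---|---|---|
| Continuous infusion | 0 h | ≥ 12 h | 12 − 0 = 12 h | No |
| Every 8 h (assumed) | 8 − 2 = 6 h to 8 − 0 = 8 h | ≥ 12 h | 4 to 6 h | No |
| Every 12 h (assumed) | 12 − 2 = 10 h to 12 − 0 = 12 h | ≥ 12 h | 0 to 2 h | Only at exactly 12 h |
| Every 24 h (assumed) | 24 − 2 = 22 h to 24 − 0 = 24 h | ≥ 12 h | none | Yes, throughout |

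In general, the latest time that 6.9.3 allows is I hours, so the rules have no common time when I is below 12. The earliest time it allows is I − 2 hours, so every permitted time satisfies 6.4.2.2 once I is 14 or more.

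**Do the scopes overlap?** Section 6.4.2.2 itself foresees thromboprophylaxis after bypass surgery, with rivaroxaban interrupted meanwhile, and its LTOLE paragraph adopts that guidance. Section 6.9.3 LTOLE names completed thromboprophylaxis as an occasion for restarting. A post-CABG subject finishing parenteral prophylaxis therefore meets the conditions of both.

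**The case against.** The strongest reply is that a specific rule governs a general one. The 12-hour gap stands in the bypass-surgery section, directly after a sentence limited to subjects scheduled for CABG, and it mirrors the post-CABG rule of the main trial. Section 6.9.3 is the general text. On that reading there is one rule after CABG and another elsewhere. This is plausible, and it does confine the problem: outside bypass surgery the protocol does not contradict itself here. But the protocol nowhere states this precedence. It uses cross-references in comparable places (Section 6.9 points to 6.9.1, and 6.9.2 points to 6.4.2.3) but has none here. A site looking up conversion from a parenteral drug would naturally turn to 6.9.3 and find nothing sending it to 6.4.2.2.

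A second reply is that the triggers differ: 6.4.2.2 speaks of initiating LTOLE treatment after surgery, 6.9.3 of restarting it. The 12-hour sentence, however, concerns any administration and is not limited to a first start.

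A third is that Section 6.4.2 describes itself as general guidance that does not displace clinical judgment. That is true, and it lowers the stakes, but it does not tell a site which of two written times was intended.

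A reader might also infer that the two rules can never both be met. The table shows otherwise: once-daily dosing meets both, and 12-hourly dosing can.

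**Conclusion.** The inconsistency is real but narrow. It concerns LTOLE subjects after bypass surgery who move from a parenteral anticoagulant to rivaroxaban. For a continuous infusion the rules are incompatible (0 h against at least 12 h), and this needs no assumption. For intermittent dosing the answer depends on intervals that the protocol does not give: conflict below 12 hours, agreement at a single point at 12 hours, and full agreement at once daily. No view is taken here on which timing is right.

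Three wider readings are tempting and are not supported.

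- *That the rules also conflict in the other direction, from rivaroxaban to an anticoagulant.* The blinded-phase text of Section 6.9.3 says "If therapeutic anticoagulation is required, subjects should start therapeutic anticoagulation immediately, irrespective of the timing of the last dose of study rivaroxaban", whereas its LTOLE text says "Discontinue rivaroxaban and give the first dose of parenteral anticoagulant at the time that the next rivaroxaban dose would be taken". These belong to different phases. Section 1.1 states that the dedicated LTOLE sections describe LTOLE activities only, and the blinded rivaroxaban/aspirin arms have been stopped. The 6.9.3 LTOLE text gives the only timing rule in that direction for LTOLE subjects. The 12-hour rule in 6.4.2.2 does not address it.
- *That the 12-hour gap is a general LTOLE rule.* It stands only in the bypass-surgery section.
- *That LTOLE bleeding results would be distorted.* The documents give no figure from which to judge this. LTOLE is uncontrolled and its analyses are descriptive, so no comparison, type I error or power is affected.

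The point is worth correcting because it is a safety instruction and the remedy is cheap.

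**What to change.** Reconcile the LTOLE text of Sections 6.4.2.2 and 6.9.3. Either state in both which rule governs a post-CABG subject coming off a parenteral anticoagulant, with a cross-reference each way, or align the wording so that both give the same timing. Which timing stands is for the sponsor's medical lead to decide.

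The cost is a wording change in two LTOLE paragraphs and a letter to sites. Data collection, sample size and analysis are unaffected.
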